7.2 Safety Assessments

Safety assessments will be conducted for all subjects at the time points indicated in Schedule of Assessments ([Table 2](#)). Safety parameters include an evaluation of AEs, focused physical examination, vital signs, and neutralizing antibody production.

7.2.1 Focused Physical Examination (FPE)

At the time points indicated in the Schedule of Assessments ([Table 2](#)), the investigator or designee will perform a FPE of the subject that includes the face, head, and neck. Further details are provided in [Appendix 7](#).

Post-baseline, the signs and symptoms will also be monitored via FPE of face, head, and neck to evaluate local effect of toxin. In addition, a general physical examination to evaluate the remote spread events will be conducted. The list of remote spread of toxin events is considered while doing clinical evaluations based on subject's symptoms and signs ([Appendix 8](#)). Directed questioning and examination will then be performed as appropriate.

The investigator may choose to investigate any other sign that he/she observes during the physical examination. Clinically significant abnormalities noted pre-injection, i.e., at the screening/baseline visits, should be recorded as medical history and assessed as to whether the abnormalities affect subject eligibility. Clinically significant abnormalities noted post-injection should be recorded as AEs.

7.2.2 Vital Signs

Evaluation of vital signs shall be performed after approximately 10 minutes rest in the sitting position. It shall include measurement of systolic and diastolic blood pressure, heart rate, and respiratory rate.

All abnormal values at the baseline visit identified as clinically significant by the investigator shall be recorded in the Medical History form.

For any clinically significant changes from the baseline visit, an AE is to be recorded.

 EST. 1981	Title 43QM2106 Clinical Study Protocol – QM1114 – GL	Doc id MA-49290
---	--	---------------------------

7.2.3 Neutralizing Antibody Testing

Subjects will have blood samples taken at baseline prior to treatment, Month 1, and Month 6 for measurement of serum neutralizing antibody testing against QM1114-DP. Additional information and detailed description of sample volumes, processing, and storage requirement will be included in a Laboratory Manual.

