Effective date: 2022-03-21 13:08

[figure not shown]
Effective

Version: 3.0

SYNOPSIS	
	
randomized and dispensed the investigational product, and will be analyzed according to the randomization scheme. The ITT population will be the primary population used for efficacy analysis.
 
 • The per protocol (PP) population is a subset of the ITT subjects who complete the Month 1 visit and have no protocol deviations that are considered to have a substantial impact on the primary efficacy outcome. • The safety population includes all subjects who were administered the study product, and will be analyzed according to as-treated principle. All safety data will be summarized descriptively based on the safety population. 
CCI

Sample Size:	
Interim Analysis:	Not applicable.

2022-03-21 13:08

[figure not shown]
Effective date:

CLINICAL STUDY SCHEMATIC AND FLOW CHART**Table 1 Clinical Study Schematic***Effective*

Version: 3.0

2022-03-21 13:08

Effective date:

Figure 1 Study Flow Chart**Effective**

Version: 3.0

GALDERMA EST. 1981	Title 43QM2106 Clinical Study Protocol – QM1114 – GL	Doc id MA-49290
------------------------------	--	---------------------------

SCHEDULE OF ASSESSMENTS

Table 2 Schedule of Assessments

Visit	Visit 1	Visit 2	Visit 3	Visit 4	Visit 5	Visit 6	Visit 7	Visit 8	Visit 9	Visits 10-14	Visit 15
1 month = 4 weeks All visit windows are calculated from Baseline/Day 0		Day 0 Baseline ¹	Day 1	Day 2	Day 3	Day 4	Month 1	Month 3	Month 6	Months 7-11	Month 12/ EOS/ET ²
Window	(≤ 2 weeks of Visit 2)						(± 5 days)	(± 5 days)	(± 5 days)	(± 5 days)	(± 5 days)
Informed Consent	X										
Demographic Data ³	X										
Medical History	X										
Previous Medication/Procedures ⁴	X										
Urine Pregnancy Test ⁵	X	X ⁷									X
Focused Physical Examination ⁶	X	X ⁷	X	X	X	X	X	X	X	X	X
Vital Signs ⁸	X	X ¹⁰	X	X	X	X	X	X	X	X	X
Inclusion/Exclusion Criteria	X	X ⁷									
Photography		X ⁷	X	X	X	X	X	X	X	X	X
CCI											
Blood sample for serum antibody testing		X ⁷					X		X		
Randomization		X ⁷									
Treatment		X									
Dispense Subject Diary Card		X									
Collect Subject Diary Card							X				
Adverse Events	X	X ¹⁰	X	X	X	X	X	X	X	X	X
Concomitant Medication/Procedures	X	X ¹⁰	X	X	X	X	X	X	X	X	X
SUBJECT ASSESSMENTS											
CCI											
GAIS			X	X	X	X	X	X	X	X	X
INVESTIGATOR ASSESSEMENTS											
CCI											

CONFIDENTIAL
Page 18 of 86

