2.1.4 Safety Objectives and Endpoints

The safety objective is to evaluate the safety of a single dose of 50U of QM1114-DP and placebo in the treatment of moderate to severe GL.

Endpoints:

- Incidence and severity of treatment emergent AEs (TEAEs)
- FPE findings
- Vital signs
- Neutralizing antibody production

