5.5 Procedures/Reasons for Subject Discontinuation

An investigator may decide to discontinue a subject from the clinical study for safety reasons.

Although the importance of completing the entire clinical study should be explained to the subject by the clinical study personnel, any subject is free to discontinue participation in this clinical study at any time and for whatever reason, specified or unspecified, and without any prejudice. No constraints are to be imposed on the subject, and when appropriate, a subject may be treated with other conventional therapy when clinically indicated.

When a subject does not complete the clinical study, he/she will be fully assessed, if such assessment is possible. The procedures designated for the Month 12/ Early Termination (ET) visit should be completed for all subjects discontinuing the clinical study and the appropriate eCRF should be completed.

All discontinuations and the reason for discontinuation are to be documented by the investigator on the exit form. For discontinuation due to an AE, the AE form is to be completed. The investigator should also ensure that the subject receives suitable therapy for the AE.

Potential reasons for discontinuation are listed below:

- **Adverse Event:** Complete an AE form.
- **Withdrawal by Subject:** Includes consent withdrawal, subject relocation, schedule conflicts, etc. Explain the reason for withdrawal in the comment section of the eCRF exit form.
- **Lost to Follow-up:** Confirmed with two documented phone calls and a certified letter (delivery receipt requested) without answer. Explain in the comment section of the eCRF exit form.

 EST. 1981	Title 43QM2106 Clinical Study Protocol – QM1114 – GL	Doc id MA-49290
---	--	---------------------------

- **Other:**

This category is to be used for a subject who discontinues due to a reason other than as specified in the predefined categories above. Explain the reason for discontinuation in the comment section of the eCRF exit form.

A subject who has been randomized and assigned a kit number/randomization number cannot be replaced by another subject if he/she discontinues the clinical study for any reason. Additional subjects could be enrolled (randomized/assigned to treatment) in order to attain the number of evaluable subjects.

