8.1.7 Month 6/Visit 9 (\pm 5 days)

The investigator or designee will:

1. Ask the subject about AEs using an open-ended question, such as “Have you noticed any change in your health since the last visit?” Record all events, as appropriate.

GALDERMA <small>EST. 1981</small>	Title 43QM2106 Clinical Study Protocol – QM1114 – GL	Doc id MA-49290
---	---	----------------------------------

2. Ask the subject about any changes in his/her concomitant therapies/procedures (added, removed or changed) since the previous visit. Record all changes.
3. Take subject photographs (refer to photo manual for complete instructions). If the subject is wearing make-up, instruct the subject to remove it prior to taking photographs.
4. **CCI**
[REDACTED]
5. Collect blood sample for neutralizing antibody testing (Section [7.2.3](#)).
6. **CCI**
[REDACTED]
(Section [7.1.7](#)).
7. Review GAIS completion instructions with the subject. Subject to complete the GAIS (Section [7.1.1](#)).
8. **CCI**
[REDACTED]
(Appendix 1).
9. **CCI**
[REDACTED]
(Appendix 2).
10. **CCI**
[REDACTED]
(Appendix 3).
11. **CCI**
[REDACTED]
(Appendix 4).
12. Obtain the subject's vital signs (blood pressure, heart rate, and respiratory rate). Vital signs are to be taken seated after 10 minutes rest (Section [7.2.2](#)).
13. **CCI**
[REDACTED]
(Section [7.1.8](#) and [Appendix 5](#)).
14. Investigator to perform a FPE ([Appendix 7](#)).
15. Schedule the next visit (Month 7/Visit 10).

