8.1.9 Month 12 or Early Termination/Visit 15 (± 5 days)

The investigator or designee will:

1. Ask the subject about AEs using an open-ended question, such as "Have you noticed any change in your health since the last visit?" Record all events, as appropriate.
2. Ask the subject about any changes in his/her concomitant therapies/procedures (added, removed or changed) since the previous visit. Record all changes.
3. If the subject is a female of childbearing potential, collect urine for UPT and complete pregnancy test. Document the result.
4. Take subject photographs (refer to photo manual for complete instructions). If the subject is wearing make-up, instruct the subject to remove it prior to taking photographs.

Version: 3.0

GALDERMA <small>EST. 1981</small>	Title 43QM2106 Clinical Study Protocol – QM1114 – GL	Doc id MA-49290
---	--	---------------------------

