8.2 Unscheduled Visits

When necessary, unscheduled visits may be conducted, in particular if an AE occurs and needs to be assessed and/or treated.

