2.5.3 Anti-drug Antibodies (ADA)

Sampling for antibody testing will be conducted at baseline Day 0, Month 1, and Month 6. The following ADA categories will be determined based on the confirmatory assay results:

- ADA positive at any point in time, baseline or post-baseline.

- ADA positive post-baseline and positive at baseline.
- ADA positive post-baseline and not detected at baseline (treatment-induced ADA).
- ADA not detected post-baseline and positive at baseline.
- Treatment-boosted ADA, defined as a baseline positive ADA titer that was boosted to a 4-fold or higher level (greater than the analytical variance of the assay) from baseline following drug administration.
- Treatment-emergent ADA positive, defined as either treatment-induced ADA or treatment-boosted ADA.
- Persistently positive ADA, defined as having at least 2 post-baseline ADA positive measurements with at least 16 weeks (112 days) between the first and last positive measurement or an ADA positive result at the last available assessment. The category may include subject meeting these criteria who are ADA positive at baseline.
- Transiently positive ADA, defined as having at least one post-baseline ADA positive measurement and not fulfilling the conditions for persistently positive. The category may include subjects meeting these criteria who are ADA positive at baseline.
- nAb positive at any point in time, baseline or post-baseline.

The number and percentage of subjects who develop detectable ADA within each ADA response category listed above will be summarized by treatment group, including ADA prevalence and ADA incidence (proportion of ADA-positive and treatment-emergent ADA-positive subjects, respectively, in the ADA Evaluatable population). The titer values of ADA-positive subjects will be summarized descriptively (using n, min, Q1, median, Q3, max) by treatment group and visit. The kinetics of ADA development will be assessed by summarizing the number and percentage of ADA-positive subjects at each visit by treatment group.

The impact of ADA on safety data (inclusive but not limited to) any AEs, any SAEs, and any adverse events of special interest (AESIs) will be evaluated by summary statistics based on ADA status.

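### No antibody sample is planned at the early-termination visit, so conversion after the last draw goes unobserved in subjects who leave before Month 6

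*Protocol*

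**What the plan says.** Protocol section 2.1.4 lists "Neutralizing antibody production" among the safety endpoints. Protocol section 7.2.3 sets the sampling times: "Subjects will have blood samples taken at baseline prior to treatment, Month 1, and Month 6". SAP section 2.5.3 repeats them: "Sampling for antibody testing will be conducted at baseline Day 0, Month 1, and Month 6". SAP section 1.5.4 gives the same three times.

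In Protocol Table 2 and SAP Appendix A, the row "Blood sample for serum antibody testing" is marked at baseline, Month 1 and Month 6. It is blank in the combined Month 12/EOS/ET column.

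For subjects who leave, Protocol section 5.5 says: "The procedures designated for the Month 12/ Early Termination (ET) visit should be completed for all subjects discontinuing the clinical study". A footnote to Table 2 softens this to completion where possible. The step list for that visit (Protocol 8.1.9) shows no blood draw, whereas the Month 6 list (8.1.7) prints it in clear: "Collect blood sample for neutralizing antibody testing". Protocol section 8.2 allows unscheduled visits but names no antibody sample, and SAP section 2.1.1 keeps unscheduled visits out of the analyses.

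SAP section 2.5.3 plans ADA incidence and prevalence, persistent and transient categories, and a table of injection-site reactions or hypersensitivity by ADA status.

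**The concern.** The early-termination visit shares a column with Month 12, which comes after the last planned antibody draw. A subject who leaves early gets the Month 12 procedures and so skips the Month 6 serum, even while present at the site. Serum that is not drawn then cannot be recovered by any later analysis.

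Three planned outputs are affected.
- **Incidence.** Conversion after the last sample is not seen in these subjects.
- **Persistence.** A leaver who was positive at Month 1 is called persistent, with no later sample to confirm or contradict it.
- **Hypersensitivity by ADA status.** A subject who leaves after such an event may have no serum taken at or after it.

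**Working it through.** The point concerns visit content, so the plan has no figure to reproduce. The timing and size can be worked out.

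**Timing.** Table 2 defines a month as 4 weeks and counts windows from Day 0. Month 1 is Day 28 and Month 6 is Day 168, each ±5 days.
- Planned gap: 168 − 28 = 140 days.
- Range with windows: 163 − 33 = 130 days to 173 − 23 = 150 days.

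| Time of leaving | Post-baseline serum under the plan |
|---|---|
| Before Month 1 | none |
| After Month 1, before Month 6 | Month 1 only (Day 23 to 33) |
| After Month 6 | both planned samples |

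**Persistence rule.** SAP 2.5.3 calls a subject persistently positive in either of two cases: two post-baseline positives at least 112 days apart, or a positive at the last available assessment. Only the Month 1 and Month 6 pair can meet the first condition (130 to 150 days). A leaver positive at Month 1 is therefore classed by the second condition alone, on one sample. A completer who is positive only at Month 6 is also classed on one sample. The difference is that, for a completer positive at Month 1, the Month 6 result decides the class.

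**Number affected.** The active arm has 90 subjects (Protocol 5.1). No dropout rate is readable, so 5%, 10% and 15% loss before Month 6 are assumptions. The upper limit is the two-sided exact 95% limit with zero positives, 1 − 0.025^(1/n), where n is the number with Month 6 serum.

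| Assumed loss | 90 × loss | n sampled | Upper limit at zero positives |
|---|---|---|---|
| 0% | 0 | 90 | 4.0% |
| 5% | 4.5 (taken as 4) | 86 | 4.2% |
| 10% | 9 | 81 | 4.5% |
| 15% | 13.5 (taken as 14) | 76 | 4.7% |

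**Expected unseen converters.** This is leavers × late conversion rate. The rate is also an assumption; 1%, 5% and 10% are shown.

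| Active leavers | 1% | 5% | 10% |
|---|---|---|---|
| 4.5 | 0.05 | 0.23 | 0.45 |
| 9 | 0.09 | 0.45 | 0.90 |
| 13.5 | 0.14 | 0.68 | 1.35 |

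**Bias.** Let d be the share who leave, and p_S and p_L the late conversion rates in stayers and leavers. The true rate is (1 − d)p_S + d·p_L.
- If only sampled subjects are analysed, the expected estimate is p_S and the bias is d(p_S − p_L). This is zero when the rates are equal.
- If leavers stay in the denominator as negatives, the shortfall is d·p_L. With d = 10% and p_L = 5%, that is 0.10 × 0.05 = 0.5 percentage points.

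The SAP does not settle which applies. Section 2.5.3 uses an ADA-evaluable population that section 2.2 does not define.

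**Outer bound.** If every unsampled active leaver were positive and no stayer were, the true late rate would be 4/90 = 4.4%, 9/90 = 10.0% or 14/90 = 15.6%, against an observed 0%. This is a limit, not a forecast.

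**The case against.** The documents agree with one another, so this is a design choice and not an error. Subjects who leave after Month 1 still have a post-baseline sample, which detects early conversion. Their adverse events are still recorded, and they enter the hypersensitivity table with their baseline and Month 1 status. Antibody results are descriptive and follow a single dose. An ET sample would not help subjects lost to follow-up, and one drawn at, say, Day 60 is no substitute for Day 168. All of this stands, and it sets the priority.

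A reader might infer more: that seroconversion is missed in the group where it matters most, so that reported incidence is understated, perhaps by a quarter to a half. The documents do not support that.
- They give no dropout rate and no expected reasons for leaving. Loss of effect is not a discontinuation category in Protocol 5.5.
- Protocol 1.1 describes an effect that usually lasts about 4 to 6 months, so fading late in this interval is expected without antibody. One subject in four receives placebo.
- At an assumed 5% incidence, 90 × 0.05 = 4.5 active converters are expected. Missing one or two of them (22% to 44%) requires leavers to convert at 1/4.5 to 2/4.5 = 22% to 44% with 5% loss, or 1/9 to 2/9 = 11% to 22% with 10% loss. That is about 2 to 9 times the assumed rate.

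Redaction is a further caution, since some steps in 8.1.9 are blacked out. The blank schedule cell, and the unredacted draw at the other sampling visits, make a hidden ET sample unlikely. The Laboratory Manual that 7.2.3 cites was not available.

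**Conclusion.** The gap is real. Followed as written, the plan takes no antibody serum at early termination. Conversion after the last sample is therefore unobserved in subjects who leave before Month 6, and those who leave before Month 1 have no post-baseline result.

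The size is modest. The count of about 4 to 14 active subjects rests on the assumed 5% to 15% loss, and precision barely changes. Differential conversion in leavers is possible but not shown. Apart from that, the only source of bias is the undefined evaluable set, which could let unsampled leavers count as negative. The persistence class of a Month 1-positive leaver rests on one result.

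This is a cheap improvement of low priority: a named safety endpoint gains data that cannot be obtained later, and the primary analysis is unaffected.

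**What to change.** **Protocol 7.2.3, Table 2 and 8.1.9, and SAP Appendix A.** Add the item "Blood sample for serum antibody testing" at an ET visit that takes place before the Month 6 sample has been drawn. Keep it subject to the existing bar on invasive procedures in pregnancy (Protocol 5.5 and 7.2.4.2.3).

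**SAP 1.5.4 and 2.5.3.** Use this sample as a post-baseline assessment with its actual study day. SAP 2.1.1 tabulates by the visit recorded on the eCRF, so say explicitly that an ET sample is not shown as Month 12 in the by-visit ADA summaries. State which post-baseline samples place a subject in the ADA-evaluable set, and how subjects without a Month 6 result are counted.

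**Cost.** A minor amendment, and one tube at a visit already planned. It takes the place of the Month 6 draw that the subject will not have, so nobody exceeds the three draws now scheduled. The downsides are a few samples at varying times with their assay cost, no recovery of subjects lost to follow-up, and conversion after the ET visit still unseen.

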7.2.4 Adverse Events

AEs are to be monitored throughout the course of the clinical study from the time the informed consent form has been signed. All AEs are to be reported on the AE form of the eCRF with complete information as required.

If AEs occur, the main concern shall be the safety of the subjects. At the time of the ICF signature, each subject must be provided with the name and phone number of clinical study center personnel for reporting AEs and medical emergencies.

At each post enrollment visit, the investigator (or sub-investigator) will question the subject about AEs using an open non-persuasive question to elicit reporting of AEs, for example “Have you noticed any change in your health since the last visit?” Additional questioning and examination will then be performed as appropriate.

7.2.4.1 Definitions

7.2.4.1.1 Adverse Events

According to International Council for Harmonisation (ICH) E2A,¹⁵ an AE is any untoward medical occurrence in a patient or a clinical investigation subject administered a pharmaceutical product and which does not necessarily have a causal relationship with this treatment. An AE can therefore be any unfavorable and unintended sign (including an abnormal laboratory finding), symptom, or disease temporally associated with the use of a medicinal (investigational) product, whether or not related to the medicinal (investigational) product.

Thus, any new sign, symptom or disease, or any clinically significant worsening of an existing sign, symptom or disease (including new episodes of a chronic disease [e.g., hay fever, allergy]) compared to the condition at the first visit, should be considered as an AE. Lack of efficacy is not considered as an AE.

Notes:

- There should be an attempt to report a diagnosis rather than the signs, symptoms or abnormal laboratory values associated with the report of an AE. However, a diagnosis should be reported only if, in the investigator's judgment, it is relatively certain. Otherwise, symptoms, signs, or laboratory values should be used to describe the AE.
- Pregnancy is not to be considered as an AE; however, is an important medical event that must be monitored as described in Section 7.2.4.2.3.

 EST. 1981	Title 43QM2106 Clinical Study Protocol – QM1114 – GL	Doc id MA-49290
---	--	---------------------------

- The effects of all BoNT products may spread from the area of injection to produce symptoms consistent with BoNT effects. These symptoms have been reported hours to weeks after injection. Remote spread of toxin that affects swallowing and breathing can be life threatening, and there have been reports of death. The risk of symptoms is increased in subjects who have underlying conditions (e.g. disorders of the neuromuscular junction) that would predispose them to these symptoms. BoNT is contraindicated in individuals with known hypersensitivity to any BoNT preparation or to any of the components in the formulation.

7.2.4.1.2 *Treatment Emergent Adverse Event*

A TEAE is an event that emerges during or after treatment, having been absent pre-treatment, or worsens relative to the pre-treatment state.

7.2.4.1.3 *Serious Adverse Events*

A SAE is any untoward medical occurrence that at any dose:

- Results in death,
- Is life-threatening,
- Requires inpatient hospitalization or prolongation of existing hospitalization,
- Results in persistent or significant disability/incapacity, or
- Is a congenital anomaly/birth defect.

Important medical events that may not result in death, be life-threatening, or require hospitalization may be considered an SAE when, based upon appropriate medical judgment, they may jeopardize the safety of the subject, and may require medical or surgical intervention to prevent one of the outcomes listed in this definition. Examples of such events are intensive treatment in an emergency room or at home for allergic bronchospasm, blood dyscrasia, or convulsions that do not result in hospitalization.

Note: The term “life-threatening” refers to an event in which the subject was at risk of death at the time of the event; it does not refer to an event which hypothetically might have caused death if it were more severe.

Inpatient hospitalization is considered to have occurred if the subject has had to stay for a night at the hospital. The criterion for prolongation of hospitalization is also defined as an extra night at the hospital. Hospitalization may not constitute sufficient grounds to be considered as an SAE if it is solely for the purpose of a diagnostic test(s) (even if related to an AE), elective hospitalization for an intervention that was already planned before subject enrolment in the clinical study, admission to a day-care facility, social admission (e.g., if the subject has no place to sleep), or administrative admission (e.g., for a yearly examination).

 EST. 1981	Title 43QM2106 Clinical Study Protocol – QM1114 – GL	Doc id MA-49290
---	--	---------------------------

7.2.4.1.4 *Unexpected Adverse Drug Reaction*

An unexpected adverse drug reaction is defined as an adverse reaction, the nature or severity of which is not consistent with the applicable study product information (e.g., IB for an unapproved investigational product).

7.2.4.1.5 *Adverse Event Reporting Period*

The clinical study period during which AEs must be reported is the period from when the subject signed the ICF to the end of the subject's participation.

The sponsor should be informed if the investigator becomes aware of any unusual safety information or any safety information that appears to be drug-related involving a subject who has participated in a clinical study, even after a subject has completed the clinical study.

7.2.4.1.6 *Severity*

Severity is a clinical determination of the intensity of an AE and not the severity of a disease.

The investigator is to classify the intensity of AEs using the following definitions as a guideline. For this classification, the investigator will take into account the possible range of the intensity of the event and report the grade of intensity which is the most appropriate according to his/her medical judgment.

Mild Awareness of signs or symptom, but easily tolerated.

Moderate Discomfort, enough to cause interference with usual activity.

Severe Incapacitating with inability to work or perform usual activity.

7.2.4.1.7 *Relationship to the Study Product and/or Clinical Study Procedure*

The investigator is to determine whether there is a reasonable causal relationship between the occurrence of the AE and exposure to the study product and/or clinical study procedure.

Medical judgment should be used to determine the relationship, considering all relevant factors including the pattern of reaction, temporal relationships, relevant medical history, and confounding factors such as co-medication or concurrent diseases.

 EST. 1981	Title 43QM2106 Clinical Study Protocol – QM1114 – GL	Doc id MA-49290
---	--	---------------------------

The expression “reasonable causal relationship” is meant to convey in general that there are facts or arguments to suggest a causal relationship (ICH E2A, Section IIIA 1).

The relationship assessment for an AE is to be completed using the following definitions as a guideline:

Reasonable Possibility: According to the reporting investigator, there is a reasonable possibility (i.e., suggestive evidence or arguments) that there is a causal relationship irrespective of the dose administered between:

- The study product (active or placebo) and the AE.
- The clinical study protocol procedure (e.g., bruising or marks from blood draws, injection related trauma, etc.) and the AE.

A two-point scale (Yes or No response) shall be used for the causality assessment. The investigator shall be asked to indicate a response to each of the following questions in the eCRF:

- “Do you consider that there is a reasonable possibility that the event may have been caused by the study product?”, and
- “Do you consider that there is a reasonable possibility that the event may have been caused by the study product injection procedure?”

If any of these questions is answered Yes, the AE is considered related.

No Reasonable Possibility: No suggestive evidence or arguments can be identified regarding a causal relationship between the study product or the clinical study protocol procedure and the AE.

